4.2.1 Access to RSBY

We evaluate three methods of accessing RSBY:

- A. Free RSBY. Households obtain access to RSBY for no charge, not even the INR typically charged to obtain a biometric, smart card that functions as the insurance card.
- B. Right to purchase RSBY and an unconditional cash transfer equal to the premium. Households obtain an unconditional cash transfer equal to the RSBY premium in their district plus the right to buy RSBY in the following 3 weeks.
- C. Right to purchase RSBY. Households receive the right to buy RSBY in the next 3 weeks, but no cash transfer, conditional or otherwise.

We compare outcomes under these conditions versus a control condition:

- D. No intervention.

We choose these interventions because they address important academic and policy questions. Programs such as RSBY in India or Medicaid in the US are actually two conceptually distinct interventions: access to insurance at full price (i.e., pure insurance) and a (conditional) cash transfer equal to the insurance premium. Moreover, different interventions have different budgetary effects; we want to net these out by comparing budget neutral alternatives such as conditional and unconditional cash transfers. We seek to value each of these interventions. These not only have different effects, they are different policy options available to the government. Comparing condition C to condition D yields the value of pure insurance. Comparing condition A to C yields the value of a conditional cash transfer. Finally, comparing conditions A and B yields the difference between a conditional and an unconditional cash transfer.

5 Evaluation Design

We carried out a randomized controlled trial (RCT) to test the impacts of the RSBY expansion to APL households.

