5.2 Treatment assignment

We designed a two-stage randomization process to study both direct treatment and spillover effects of health insurance.

In a first stage, we randomly assigned villages to one of five village-level arms. A village-level arm is defined by the percentage of households within the village assigned to each of the four household-level study arms defined in subsection 4.2.1. The percentage allocations to the 4 household-level arms are given in the last 4 columns of Table 1. The percent of villages assigned to each of the 5 village-level arms are in the second column. Villages were matched before this first stage randomization.⁷

Table 1: IHIE Two-Stage Randomization Design

Village-level arms (%)		Household-level arms (%)			
Arm	Village allocation	Group A	Group B	Group C	Group D
I	15	30	50	10	10
II	15	30	10	50	10
III	15	30	10	10	50
IV	35	70	10	10	10
V	20	10	30	30	30
Total	100	40	20	20	20

In a second stage, we randomly assigned households within a village to the four arms according to the allocation probabilities assigned to the village. Households were matched before this second stage randomization.⁸

The target enrollment for each of the 4 household-level arms, unconditional on village-level arm, was 4,500 households for condition A and 2,250 households for each of conditions B, C and D. Due to some attrition between listing and completion of baseline, our final randomized sample amounted to 11,089 households in 424 villages in the two districts.

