In addition, we will estimate two substantively different specifications to abstract away from methods of access to insurance and towards the mere fact of access to insurance. On one, we replace the four household group indicators with an indicator for whether the household was in group A, B or C and we replace the four village-level arm share variables with the share in groups A, B or C.¹¹ Additionally, we will estimate a specification where σ_j^v is replaced by the total share of the village eligible for RSBY, including both the share assigned to A, B and C as well as the share of the village with BPL cards or in certain eligible occupational classifications (who were therefore RSBY eligible).

Control variables. We first estimate a variant of the regression model above without any controls X_{ijs} , where s indicates a time that may not be equal to t . We then estimate a specification where X_{ijs} is a vector of baseline controls (i.e., X_{ijs} at time $s = 0$). We will use machine learning methods to select these control variables. Finally, we will run specifications where X_{ijs} may include so-called “coloring variables” that shed light on mechanisms of impact, welfare effects, and the dosage of treatment. In the latter case, we will include interactions of treatment variables with coloring variables, the same manner in which we estimate heterogeneous treatment effects. These coloring variables are listed in section 8.

Weighting. This regression can be weighted in multiple ways. We could either weight each household equally or weight each village arm identically. When examining household-level access We choose to weight each household equally because no household is obviously more informative than any other, especially when examining questions about the impact of insurance on households. When examining spillovers, we will weight villages equally.

Standard errors. We use the cluster robust HC2 standard errors at the village level. [name], Jiang, and [name] (2019) shows that this is a conservative variance in two-stage randomized experiments.

Spillovers. To address the possibility of spillovers from, e.g., giving some households access to insurance in one way affects households not given access to insurance in that way, we do a few things.

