First, we measure ITT effects accounting for spillovers at the village level by examining the predicted effects on outcomes for a household in a given group at different shares of the village sample in that group. The specific shares selected could be in-sample shares or out-of-sample shares. We will highlight when we make out-of-sample predictions.¹² In cases where we want to report ITT under sample average spillovers, we will exclude interaction between household arms and, e.g., village arms.

Second, we make assumptions required for unbiased estimation of, (γ_h, λ_{hv}) with spillovers as given in [name], Jiang, and [name] (2019). The key assumption is partial non-interference, i.e., assignments in villages $j' \neq j$ do not influence outcomes in another village j .

Third, to test for the existence of spillover effects, we conduct the Wald test with the null hypothesis that $\beta_v = \beta_{v'}$ and $\lambda_{vh} = \lambda_{v'h}$ for any $v \neq v'$ and $h = 1, 2, 3, 4$. This test can be conducted for both take-up and any outcome variable of interest.

¹⁰<https://imai.fas.harvard.edu/research/files/spillover.pdf>.

¹¹Berry et al. (2018) consider different subsidies and associated extrapolation issues.

¹²Although our study varies the fraction of subjects in a village who receive access to insurance in some form, we do not – as Table 1 shows – give some treatment to no households or some treatment to all households. Therefore, to estimate the above parameter of interest we have to make out-of-sample predictions.

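### Dropping the household-arm by village-arm interactions yields a sample-average ITT in general only if effects are constant across village arms; otherwise each coefficient mixes in other arms' effects and uses unstated weights

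*Combined protocol and SAP*

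**What the plan says.** The basic ITT models in Section 7.1, equations (1) and (2), include interactions between household arm and village arm (or village shares). For a single figure per arm, the Spillovers paragraph gives this rule: "In cases where we want to report ITT under sample average spillovers, we will exclude interaction between household arms and, e.g., village arms". The plan does not say over which mix of village arms the average is meant to run. It also does not make the rule depend on the Wald test for spillovers described in the same part of the section.

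The Weighting paragraph sets observation weights only: "We choose to weight each household equally because no household is obviously more informative than any other".

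In Section 5.2, "we randomly assigned households within a village to the four arms according to the allocation probabilities assigned to the village". Those probabilities differ between village arms. Three rows of Table 1 (village arm, per cent of villages, then per cent of households in A, B, C, D) read "II 15 30 10 50 10", "III 15 30 10 10 50" and "IV 35 70 10 10 10".

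Two other places matter. Section 4.2.1 compares the arms with each other, for example "Comparing condition A to C yields the value of a conditional cash transfer". Section 7.1 also plans a pooled access model: "we replace the four household group indicators with an indicator for whether the household was in group A, B or C".

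**The concern.** The two-stage design exists because the effect of access may depend on how many neighbours also have access. If it does, a model that keeps village terms but drops the interactions fits one common effect per arm to effects that are not common. With three treated arms and allocations that vary by village arm, least squares then does two things. It lets the coefficient for one arm absorb variation in the other arms' effects. It also weights each arm's own village-arm effects by the amount of arm contrast they contain, not by how common those villages are.

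At stake is the meaning of any single ITT reported per arm, and of differences between them. Arms A and C could have the same effect in every village arm and still receive different coefficients.

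**Working it through.** **Inputs.** Table 1 in Section 5.2: village shares p = 0.15, 0.15, 0.15, 0.35, 0.20 for arms I to V, and household shares s(v,h). Least squares with equal household weights, from Section 7.1. Assumed: village terms kept (the rule removes only the interaction), no covariates, and equal mean village size across village arms, which the stratification on village size makes plausible. All effect sizes below are assumed.

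**Step 1, the plan's own totals.** Summing p(v) x s(v,h) over village arms gives 0.40, 0.20, 0.20, 0.20. Times 11,250 households this is 4,500, 2,250, 2,250, 2,250. Both match Section 5.2.

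**Step 2, the no-interaction coefficients.** Remove the village-arm means from the arm indicators. The cross-product matrix for A, B, C has diagonal terms sum of p s(h)(1 - s(h)) and off-diagonal terms minus sum of p s(h) s(k):

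- A row: 0.186, -0.062, -0.062
- B row: -0.062, 0.138, -0.038
- C row: -0.062, -0.038, 0.138

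Its inverse has A row 9.164, 5.682, 5.682, B row 5.682, 11.364, 5.682 and C row 5.682, 5.682, 11.364. The loading of coefficient h on arm k's effect in village arm v is p(v) times the sum over l of inverse(h,l) x s(v,k) x (1[l=k] - s(v,l)). Two examples:

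- B on its own effect in arm I: 0.15 x (11.364 x 0.25 - 5.682 x 0.15 - 5.682 x 0.05) = 0.256.
- B on A's effect in arm I: 0.15 x (5.682 x 0.21 - 11.364 x 0.15 - 5.682 x 0.03) = -0.102.

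All loadings:

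| Coefficient, effect | I | II | III | IV | V |
|---|---|---|---|---|---|
| A on A | 0.135 | 0.135 | 0.238 | 0.395 | 0.097 |
| A on B | -0.036 | -0.007 | +0.027 | -0.065 | +0.081 |
| A on C | -0.007 | -0.036 | +0.027 | -0.065 | +0.081 |
| B on B | 0.256 | 0.085 | 0.119 | 0.199 | 0.341 |
| B on A | -0.102 | 0 | +0.102 | 0 | 0 |
| B on C | -0.034 | 0 | +0.034 | 0 | 0 |
| Village allocation | 0.15 | 0.15 | 0.15 | 0.35 | 0.20 |

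The C coefficient mirrors B with arms I and II exchanged. Own-effect rows sum to 1 and cross-arm rows to 0 (within rounding), so constant effects are recovered exactly. The share version, equation (2) without interactions, gives the same loadings, because the mean of each arm indicator in a village arm is the share itself.

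**Step 3, illustrations.**

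- *Effects of 5, 4, 3 points at 50%, 70%, 90% access, the same for A, B and C.* Access is 90% in I, II and IV, 50% in III and 70% in V. Target at the village allocation: 0.65 x 3 + 0.15 x 5 + 0.20 x 4 = 3.50. Coefficients: 3.84, 3.85, 3.85. Own-effect weights alone give 3.57, 3.58, 3.58, so about 0.27 of each gap of about 0.35 is cross-arm loading.
- *B and C have effect 1 in arm IV only; A has none.* A's coefficient is 2 x (-0.0654) = -0.13; its true ITT is 0.
- *A, B and C all have effect 5 - 5 x A share.* Coefficients are 3.23 (A) and 3.44 (C), so A minus C is -0.21 instead of 0. If B's effect is zero instead, A's coefficient is 3.02 and A minus C is -0.42.

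**Step 4, pooled access model with its interaction also dropped.** Weights are proportional to p a(1 - a), with a the access share: 0.0135, 0.0135, 0.0375, 0.0315, 0.042, sum 0.138. This gives 0.098, 0.098, 0.272, 0.228, 0.304.

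**Step 5, cost of fixed weights.** Take unit residual variance, no clustering and N = 11,089 x 0.9 = 9,980, using the 10% attrition allowance in Section 5.1.

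- No-interaction SE: sqrt(9.164/9,980) = 0.0303 (A); sqrt(11.364/9,980) = 0.0337 (B, C).
- Fixed-weight SE: sqrt of the sum of p(1/s(h) + 1/s(D)), divided by N. The sums are 11.467 (A) and 14.933 (B, C), giving 0.0339 and 0.0387.
- Ratios: 1.12 and 1.15.

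**The case against.** The strongest reply is that the rule covers an optional summary. The basic models are interacted, the predictions at chosen shares are unaffected, and the Wald test looks for variation across village arms. All of that stands. A reader might infer that the plan's ITT analysis as a whole is biased; the documents do not support this. The problem is confined to the single figure per arm produced by the reduced model.

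A second reply is that the plan never defines its sample average, so 3.50 is only one benchmark. That is fair. In the 5/4/3 case, averaging over each arm's own households gives 3.28, 3.45, 3.45, and averaging over control households gives 4.05. The coefficients lie within that range but equal none of these. The loading on other arms' effects, moreover, belongs to no reading of an average of one arm's own effects.

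A third reply is precision. The reduced fit has lower mean squared error while its gap stays below sqrt(0.0339² - 0.0303²) = 0.015 SD for A, or sqrt(0.0387² - 0.0337²) = 0.019 SD for B and C, before clustering. At an assumed outcome SD of 30 to 50 points that is about 0.5 to 0.8 and 0.6 to 0.9 points, so it would do better in the 5/4/3 case. This stands, and is the reason to keep that fit.

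Two further inferences go too far. The pooled access model is not affected as written, because substituting one indicator and one share into equation (2) keeps the interaction; it is affected only if the exclusion rule is applied there too. And differing village mixes are not the main cause in the 5/4/3 case, where cross-arm loading makes up about 80% of the gap.

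**Conclusion.** The concern holds in this limited form. Under Table 1, excluding the interactions returns the sample-average ITT in general only when effects do not vary by village arm; exact agreement otherwise needs a chance cancellation. When effects vary, the coefficients for A, B and C load on one another's effects and use different own-effect weights, none equal to the village allocation.

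The loadings follow from Table 1 and the assumptions listed with the inputs. The gaps (about 0.35 points in the 5/4/3 case, -0.13 for an arm with no effect, -0.21 or -0.42 for A minus C) rest on assumed effect patterns and are illustrations, not forecasts. It is more than a missing definition, because the stated rule fails under the kind of variation the two-stage design was built to study. It should be corrected before analysis, but it does not invalidate the randomization, the interacted models or the share-based predictions.

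**What to change.** Wherever one sample-average ITT per arm is reported, compute it from the already planned interacted model (1): take the five within-village-arm contrasts against D and average them with weights written into the plan. These would be 0.15, 0.15, 0.15, 0.35, 0.20 or the realised household shares of the village arms. An equivalent form omits one village indicator and centres the others at those weights. This carries no cross-arm loading. Do the same for the pooled access indicator.

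Report the no-interaction coefficient beside it, labelled as a regression-weighted summary that equals the sample-average ITT in general only if effects are constant across village arms.

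No new data are needed. The price is precision: standard errors about 12% larger for A and 15% for B and C before clustering, or 25% and 31% more variance (about 10% larger SE for the pooled model). With an assumed village ICC of 0 to 0.10 and a village-by-arm ICC of 0 to 0.05, the rise in SE is 6 to 12% for A and 8 to 15% for B and C.

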7.2 Complier average treatment effect (CATE)

Our second parameter of interest is the CATE estimate for the impact from uptake of insurance. Our basic regression model to estimate this has a two-stage least squares structure:

$$y_{ijt} = \alpha + \theta s_j + \phi z_{ij} + \rho s_j z_{ij} + \psi X_{ij} + u_{ijt} \quad (3)$$

where z_{ij} is the binary enrollment variable by household i in village j , and $s_j = \sum_{i=1}^{n_j} z_{ij}/n_j$ is the enrollment rate in village j . We estimate this equation using instrumental variables, d_j^v , d_{ij}^h , and $d_j^v d_{ij}^h$ (see Appendix E.2 of [name], Jiang, and [name] (2019), for $(s_j, z_{ij}, s_j z_{ij})$). The remaining variables are defined as in equation (2). In particular, the control variables and weighting are managed as they are in the previous section.

Identification. The exclusion restriction for CATE estimation is that treatment assignment only affects household outcomes through the decision to enroll in RSBY (see [name], Jiang, and [name] (2019) for details). Note we are not instrumenting *utilization* of RSBY, which would require a stronger exclusion restriction. We are instrumenting enrollment in RSBY.

Spillovers. To address the possibility of spillovers, we do many of the things we do for the ITT analysis. For example, as discussed by [name], Jiang, and [name] (2019), we will use the cluster robust HC2 variance or the weighted average of individual and cluster robust HC2 variances. The most important difference is the assumptions required for unbiased estimation with spillovers, as given in [name], Jiang, and [name] (2019). Beyond partial non-interference as before, we must assume that for noncompliers their treatment assignment does not affect their outcome through the enrollment of other units. Moreover, we test for the existence of spillovers by testing the null hypothesis that $\theta = 0$ and $\rho = 0$.

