Trial registration. The IHIE was registered with the American Economics Association (AEA) Registry (RCT ID: AEARCTR-0001793) on December 16, 2016 (before the 18 month follow-up) and at ClinicalTrials.gov (ID: NCT03144076) on May 8, 2017. We did not register prior to these dates as it was not the norm in the economics literature to register experiments prior to initiation.

3 Evaluation questions

The IHIE was designed to address the following questions.

1. What is the value of health insurance in a developing country context? Specifically, what is the value of expanding eligibility for RSBY to the non-poor?

Within this broader question we address the following specific questions:

- (a) Does access to insurance or insurance itself increase utilization?
- (b) How does access or insurance affect health through increased utilization?
- (c) Does access or insurance affect health independent of utilization, perhaps through a "peace of mind" effect?
- (d) How does access or insurance affect a household's finances, its asset portfolio, its income, its consumption or the variability of its consumption through increased utilization?
- (e) Does access or insurance affect finances independent of utilization, perhaps by altering a household's portfolio and thus its income and consumption?
- (f) Is there an income effect from health care or health care financing (capital) costs?
- (g) Is there an income effect from health insurance premium subsidies?

When exploring these questions we address a number of other cross-cutting questions:

2. Do insurance prices affect utilization, and if so how?
3. Are there spillover effects on non-beneficiaries, or spillovers within beneficiaries?
4. Does access to insurance affect intra-household allocation of resources? How are the benefits of health insurance distributed within the household?

4 Intervention

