5.4 Treatment Delivery

The population that is eligible for this study would not be eligible for RSBY under the program's usual rules. To make this study possible, we exchanged letters of cooperation with the state in which we conducted the study (Karnataka), the central government agency (Ministry of Labor) responsible for administration of RSBY, and the development organization (GIZ) providing technical support for RSBY.

Sample households were randomized in August 2014 using data from the listing exercise. They were informed of their treatment assignment and, depending on which arm to which they are assigned, given access to insurance or cash in May and June 2015. This step took place roughly 18 months after the baseline due to government constraints. Due to challenges associated with evaluating a government program, we were only able to enroll sample households when the government held its RSBY enrollment drive in early 2015.

We enrolled study households much in the same way the government enrolled RSBY (non-study) eligible households into the program: via a mobile enrollment truck that visited each village. One difference is that we went to each household to ask them if they would like to enroll and took them to the enrollment truck, which was parked in one place in the village. By contrast, the government informed non-study households by delivering paper notices (chits) to each home about when and where the enrollment truck would be in the village.

Roughly 78.4%, 70.4% and 58.6% of households in arms A, B, and C, respectively enrolled in RSBY. Enrollment rates are somewhat higher in Gulbarga than Mysore: 77.9/76.4/64.1% v. 78.8/63.5/52.3% in A/B/C. No one in arm D enrolled.

For all study households that take up insurance, we paid the government their premiums. For households in arms A, this was funded by grant funds. For those in B and C that purchase insurance, this was funded by the respondents' money.

The Karnataka government renewed RSBY automatically for non-study and study households in 2016 and 2017 without any action—even payment—by enrollees. RSBY ended in the state on August 31, 2018, to make way for the new NHPS scheme, which is scheduled to start in late 2018 or early 2019. As of this writing, Karnataka had agreed to roll out NHPS but had not begun the roll-out.

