8.5 General coloring variables

The following is a non-exhaustive list of variables that may be used as control variables that measure dosage, specific margins of response or dosage. This list is non-exhaustive as it lists only those variables measured at endline and not otherwise included as a coloring variable above.

- Gender of respondent
- Age of respondent
- Role of respondent in household (relationship to head of household)
- Size of household
- Number of adults in household
- Number of children in household
- Knowledge of BPL households and how many
- Knowledge of BPL households with RSBY cards and how many
- Knowledge of household that successfully used RSBY
- Knowledge about RSBY (number correct out of 4 questions)
- Knowledge of when RSBY scheme expired
- Subjective willingness-to-pay for RSBY
- Knowledge about NHPS
- Does respondent think household is covered by NHPS
- One item test of NHPS (does respondent know about amount of coverage)
- Did any other individuals assist with answering questions during the survey? If so, what is the gender and relationship to respondent? ¹⁷

¹⁷Additional respondents may affect the response quality in both positive and negative ways. For finance questions, these individuals may improve the precision of the responses. For health questions, these individuals may lead to decreased precision. Please note that enumerators were instructed to administer health questions without any additional individuals present to minimize this concern.

9 Structural modeling

We plan to develop an economic model of household financial decisions and health status. We will structurally estimate the model using the experimental variation, to quantitatively reconcile the rich set of empirical results and perform counterfactual analysis.

10 Why is higher price for insurance associated with higher utilization?

At midline we found that individuals in group C, which had to pay a premium for insurance but did not get an unconditional cash transfer, had higher rates of utilization of the RSBY card. We will explore three explanations. First, individuals that value insurance more because they are more likely to use it are more likely to take up insurance, i.e., there is selection. Second, a higher price for a good sends a positive signal about the quality of the good, and higher quality goods are consumed more. Third, there is some sunk cost effect.

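### The CATE model treats arm B assignment as an excluded instrument for enrolment, although arm B households receive cash whether or not they enrol

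*Combined protocol and SAP*

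**What the plan says.** Section 7.2 defines the plan's second parameter of interest, the effect of taking up insurance. Equation (3) has one binary enrolment variable, the village enrolment rate s_j and their product, with coefficients phi, theta and rho. The instruments are the village-arm indicators, the household-arm indicators and their products, with no arm left out. Identification rests on the statement that "treatment assignment only affects household outcomes through the decision to enroll in RSBY". The only caveat offered is that enrolment, not utilization, is instrumented.

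Section 4.2.1 describes arm B: "Households obtain an unconditional cash transfer equal to the RSBY premium in their district", with the right to buy in addition. Section 5.4 says of premiums: "For those in B and C that purchase insurance, this was funded by" the households themselves. It also reports uptake: "Roughly 78.4%, 70.4% and 58.6% of households in arms A, B, and C, respectively enrolled in RSBY". Nobody in D enrolled.

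Section 3, question 1(g), asks: "Is there an income effect from health insurance premium subsidies". Section 4.2.1 uses A against B to compare conditional with unconditional cash. Section 11.1 takes spillover estimates from the CATE analyses as well as from the ITT analyses.

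**The concern.** For arm B, assignment delivers two things: the right to buy insurance, and cash that does not depend on buying it. Enrolled B households paid their premium from their own money. The 29.6% who did not enrol therefore kept the cash without insurance. With B at 20% of the sample, that is 0.296 × 0.20 = 5.9% of all households. For them, assignment changed something other than enrolment, by design.

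The ITT model leaves the cash effect free to be estimated. Section 7.2 fixes it at zero without argument. If it is not zero, part of it is reported as an effect of enrolment and part appears in theta and rho, the coefficients that Section 7.2 tests for spillovers.

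**Working it through.** **Inputs.** Village-arm weights (15, 15, 15, 35, 20%) and household shares come from Table 1. Enrolment of 0.784, 0.704, 0.586 and 0 in A, B, C and D comes from Section 5.4. Three assumptions are needed: each household arm's enrolment rate is the same in all village arms, mean village size is equal across village arms, and B's cash has a direct effect delta on every B household. The documents do not give delta, so results are per unit of delta.

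**Check of the design figures.** Weights times shares give 40/20/20/20%. On 11,250 households this is 4,500/2,250/2,250/2,250, which matches Section 5.2.

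**Village enrolment.** s_j is the share-weighted mean of the arm rates. For village arm I: 0.3 × 0.784 + 0.5 × 0.704 + 0.1 × 0.586 = 0.646. Arms I to V give 0.646, 0.599, 0.364, 0.678 and 0.465, with a weighted mean of 0.572.

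**Bias.** With indicators and products as instruments, the first stage is saturated. Two-stage least squares then reduces to weighted least squares on the 20 village-arm × household-arm cells, regressing the outcome on 1, s, z and s·z at their cell means. Setting the outcome to 1 in B cells and 0 elsewhere gives the loading on delta.

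| Enrolment rates | theta | phi | rho | phi + rho·s at mean s | Range over village arms |
|---|---|---|---|---|---|
| Overall | +0.26 | +0.95 | −1.12 | 0.305 | 0.19 to 0.54 |
| Gulbarga | −0.08 | +0.66 | −0.43 | 0.40 | 0.36 to 0.50 |
| Mysore | +0.59 | +1.17 | −1.79 | 0.20 | −0.02 to 0.54 |

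For the first row, 0.946 − 1.122 × 0.5716 = 0.305. The sign of the theta bias is not fixed. If cell enrolment varies by ±5 points, the central 95% of draws for the loading at mean s is 0.22 to 0.40.

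**Scale.** If only B non-enrollees' INR 200 counts, the bias on a money outcome is 0.305 × 0.296 × 200 = INR 18. With 424 villages of 26 households and an assumed intracluster correlation of 0 to 0.10, the standard error at mean s is 0.036–0.037 SD. A delta of about 0.12 SD would therefore shift the estimate by one standard error. For intracluster correlations of 0.02 to 0.10, the test of theta = rho = 0 rejects about 5%, 7% and 12–14% of the time at deltas of 0.05, 0.1 and 0.2 SD.

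**Effect of the fix.** With a B indicator as regressor, or with B dropped, the delta loading is exactly 0 in theta, phi and rho. The standard error rises 2.0–3.4% with the indicator and 2.6–3.9% with B dropped.

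**What the fix does not change.** The same regression gives the weights that the enrolment effect at mean s puts on the per-enrollee effects of A, B and C:

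| Fit | A | B | C |
|---|---|---|---|
| Plan | 0.80 | 0.21 | −0.02 |
| B indicator | 0.96 | 0 | 0.04 |
| B dropped | 0.95 | 0 | 0.05 |

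Now suppose A and C differ. If card use per assigned household were merely equal in the two arms, C's per-enrollee rate would be 0.784/0.586 = 1.34 times A's. With B's per-enrollee effect equal to A's and no true spillover, spurious rho, in multiples of A's effect, is −0.42 under the plan, −0.49 with the B indicator and −0.55 with B dropped.

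**The case against.** The strongest reply is that the cash is trivial: about INR 200, once, in May–June 2015, against an endline in March–May 2019. No value of delta is given, the spillover test stays near its nominal level for small deltas, and a plan may adopt a stated identifying assumption. The point about size stands. A reader might infer that the CATE is materially wrong, and the documents do not support that. But the plan does not offer this argument, its own questions treat the cash effect as open, and Appendix 1 says the same plan guides analysis of the 12- and 18-month surveys, when the payment was more recent.

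A reader might also infer that Section 7.2 errs by having no CATE for each arm, since footnote 19 mentions CATE estimates for A and for C. It does not. The section defines a single uptake effect, the footnote is an aside, and no test listed in Section 10.2 depends on it.

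It is also tempting to object that the pooled effect gives C almost no weight, given that "Comparing condition C to condition D yields the value of pure insurance". The figure is right, but the ITT model carries the C against D contrast, and the fix leaves C's weight at 0.04–0.05.

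Two further objections stand. The fix somewhat enlarges spurious rho if A and C differ per enrollee. The midline report that households in C "did not get an unconditional cash transfer, had higher rates of utilization of the RSBY card" makes equality doubtful for that outcome. Secondly, s_j pools enrollees of all arms. If only C enrollees generated spillovers, even a separate A against D fit would return a spurious rho (−0.27 per unit).

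C enrollees' own payment, by contrast, is a difference in what enrolment means, not an exclusion failure, because it occurs only through enrolling.

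**Conclusion.** The concern holds. The exclusion statement in Section 7.2 conflicts with the content of arm B in Section 4.2.1, and nothing in the plan reconciles them. The bias in the enrolment effect is about 0.31 delta at mean village enrolment, 0.19 to 0.54 delta across village arms, and theta and rho are biased as well. These loadings rest on Table 1, the Section 5.4 rates and the assumption that enrolment by household arm is constant across village arms. Delta itself is unknown, may be small at four years, and is zero for any outcome the cash does not move. ITT estimates, including the A against B and C against D contrasts, are untouched. This should be fixed because the contradiction is plain and the remedy cheap, not because a large error has been shown.

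**What to change.** 1. Limit the exclusion statement to A and C against D.
2. Enter the arm B indicator as an included regressor in equation (3), which suffices if B's direct effect is the same in all village arms. Otherwise drop B from the IV sample.
3. Report the plan's all-instrument fit alongside as a sensitivity analysis.
4. State the limits of the revised model. Its CATE is about 95% weighted to arm A. The theta/rho test still assumes equal per-enrollee effects in A and C (spurious rho of −0.49 to −0.55, against −0.42 under the plan, if C's is 1.34 times A's), equal spillovers from A, B and C enrollees, and no village-level effect of B's cash.

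Separate A against D and C against D fits are optional supplements. They relax the equal A and C effects assumption but not the other two. The C against D standard error would be about 1.5–1.6 times the pooled one, and the A against D one 5–8% larger. If an overidentification test is added, a rejection should not be read as proof of exclusion failure, because compliers in A (78.4% enrolled) and C (58.6%) may differ.

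The cost is plan wording, one extra regression per outcome on data already planned, and a standard error about 2–4% larger.
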